6.5.10.5.7 Lens Status – Deposits

Lens deposits, including type, percentage coverage, and degree, will be collected at the eye level for study lenses at all follow-up visits.

Page 23 of 44 - CONFIDENTIAL

Deposit type is identified by the following categories:

- None
- Crystalline deposits
- Crust-like deposits
- Film
- Spots

If deposit existence is confirmed, percentage coverage and degree will be assessed by the below categories:

Percentage Coverage:

- 1 25%
- 26 50%
- 51 75%
- 76 100%

Degree:

- Light
- Medium
- Heavy

Lens deposit data will be summarized categorically at the eye and subject level by visit and visit type (unscheduled/scheduled). Eyes/subjects with multiple visits in a visit category will be counted once for the worst category. The Total column will summarize the worst case over scheduled and unscheduled visits for each visit category. In addition, a summary over all follow-up visits for both deposit coverage and degree of deposits will be performed using the worst case over all follow-up visits.

Lens deposit data will be presented in a worn lens evaluation listing.

6.5.10.5.8 Lens Characteristics

Lens characteristics including wettability, centration, and movement will be collected for dispensed study lenses at the Screening/Dispensing Visit and for worn study lenses at other visits. Data will be collected at the eye level. Data will be summarized categorically by visit and visit type (unscheduled/scheduled) at both eye level and subject level. The percentages will be based on the number of eyes/subjects with responses. A total column will be added to summarize the worst case over scheduled and unscheduled visits. In addition, a summary over all follow-up visits will be conducted for study lenses using the worst case over all follow-up visits.

Page 24 of 44 – CONFIDENTIAL

Subject listings will also be presented.

6.5.10.5.8.1 Wettability

Lens wettability will be assessed at each visit on the following scale:

- 100% of anterior lens surface is wettable
- Presence of small (<0.1 mm), individual discrete non-wetting areas
- Presence of single area of non-wetting between 0.1 mm and 0.5 mm in size
- Presence of several areas of non-wetting between 0.1 mm and 0.5 mm in size
- Presence of one or more non-wetting areas greater than 0.5 mm in size

6.5.10.5.8.2 Centration

Lens centration will be assessed at each visit on the following scale:

- Grade 0 (Equal Overlap 360 degrees)
- Grade 1 (Maximum overlap less than or equal to 2/3 in any sector)
- Grade 2 (Maximum overlap greater than 2/3 in any sector)
- Grade 3 (Any Corneal Exposure)

6.5.10.5.8.3 Movement

Lens Movement will be assessed at each visit on the following scale:

- Grade -2 (No observable movement)
- Grade -1 (Minimal; Just observable movement, lens returns to origin)
- Grade 0 (Free movement, lens returns to origin)
- Grade +1 (Substantial movement; but lens does not immediately return to origin)
- Grade +2 (Excessive movement; lens does not return to origin, may result in corneal exposure)

The order of severity for lens movement from worst to best is: -2, +2, -1, +1, 0.

The Josephson Push-Up Test will be used if lens movement is rated as -2 = No observable lens movement and rated as:

- Lens is mobile
- Lens is immobile (the worst case)

6.5.11 Statistical/Analytical Issues

6.5.11.1 Handling of Dropouts or Missing Data

The primary efficacy analysis will be conducted using the FAS and missing values will not be imputed.

Page 25 of 44 – CONFIDENTIAL

Sensitivity to missing primary endpoint data will be evaluated using the following analyses:

- **Best-case analysis:** Subjects with missing responses on the statement of clear vision are imputed as 'Agree.'
- Worst-case analysis: Subjects with missing responses on the statement of clear vision are imputed as 'Disagree.'
- **Tipping point analysis:** if the primary efficacy analysis shows statistical significance and the worst-case analysis does not, a tipping point analysis will be performed using the following procedures:
 - a. Impute any one missing value as 'Disagree,' and rest of missing value as 'Agree.'
 - b. Using the imputed dataset from step a, perform the one-sided exact binomial test and determine statistical significance based on the resulting p-value.
 - c. Repeat steps a and b until conclusion reversed or until all data are imputed as 'Disagree.'

Only subjects who did not provide a response to the primary endpoint question, including those who attended the 3-Week Visit but did not fill out the questionnaire, will participate in the sensitivity analyses. Subjects who provided a response of "neither agree nor disagree" will not be included. For Best-case and Worst-case analysis, the number of imputed subjects will be displayed with the number of non-imputed subjects. 95% confidence interval from an exact binomial (Clopper-Pearson) test will be presented with p-value from a one-sided exact binomial test of the alternative hypothesis that the proportion of subjects agreeing is greater than 0.5.

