### **3.3.3 Subject Discontinuation**

A subject MAY be discontinued (at the discretion of the Investigator, the Sponsor, and/or the IRB) prior to the final study visit for a variety of reasons, including, but not limited to:

- An AE occurring during the course of the study, which precludes continued treatment or follow-up

- Persistent Grade 3 or 4 slit lamp findings
- Persistent study-related symptoms/complaints
- Unacceptable contact lens visual acuity (VA)
- Unacceptable contact lens centration
- Unacceptable contact lens movement
- Failure to follow study procedures

A subject MUST be discontinued prior to the final study visit for any of the following reasons:

- Voluntary withdrawal
- Death
- Investigator decision that it is not in the best medical interest of the subject to continue participation in the investigation
- Lost to follow-up ([Section 3.3.4](#))
- Either eye is discontinued
- Becomes pregnant during the study

Prior to discontinuing a subject, every effort should be made to contact the subject, schedule a final study visit, obtain as much follow-up data as possible, and retrieve all study materials. Adverse events will be followed as described in [Section 6.0](#).

Subject discontinuations must be documented clearly on the source document and applicable eCRF. The Investigator should indicate the PRIMARY (one) reason that the subject was discontinued for each eye. Subjects who voluntarily withdraw from the study are not required to provide a reason for their decision but should be encouraged to share this information. Subjects who are discontinued from the study following enrollment will not be replaced.

Exit Visit assessments should be completed for early discontinued subjects, if possible.

At the final study visit, all study subjects who are discontinuing should be examined to ensure that their ocular health is consistent with pre-study, baseline conditions. Any adverse effects determined to have been reasonably caused by participation in the study will be followed per the standard of care. Participation in the study will not impact post-study choices of study subjects for correcting their vision using marketed products (e.g., contact lenses and contact lens care solutions).

Whether a subject completes or is discontinued from the study, they will be directed by the Investigator to resume their habitual method of vision correction.

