#### **5.1.4 Exit Visit**

***Note: All VA measurements MUST be made using a phoropter.***

- a. Indicate status of the subject on the Subject Exit Form. If the status is “Discontinued” or “Non-dispensed,” indicate the PRIMARY exit reason for each eye on the Subject Exit Form.
- b. Collect changes in ocular medical history and concomitant medications
- c. For all subjects, complete an exit ocular examination without lenses on the eyes. Collect the following assessments:
  - Spherocylindrical refraction
  - High-contrast distance (OD, OS, OU) logMAR BSCVA
  - Keratometry

Compare the final visit high-contrast distance (OD, OS) BSCVA to the high-contrast distance (OD, OS) BSCVA obtained at the Screening/Dispensing Visit. If the VA has decreased by  $\geq 10$  letters, explain.

For each eye, compare the final visit keratometry readings to the Screening/Dispensing Visit keratometry readings. If there is a change of 1.00 D or more, explain.

- d. Collect/assess all AEs/ADEs, including serious or significant non-serious AEs.
- e. Collect all worn and unworn study lenses from the subject.

***Note: The Investigator must return all worn and unworn study lenses to the Sponsor in the return materials provided. All study contact lenses must be accompanied by a Product Accountability Log.***

- f. Complete the Investigator survey following the completion of the subject’s final study visit.
- g. Complete the Exit visit eCRFs.

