6.5 Statistical Methods

6.5.1 Data Sets Analyzed

The Full Analysis Set (FAS) will consist of all eligible, dispensed subjects or eyes. If only one eye is dispensed, the subject will be included in the FAS for subject level analyses, but only the dispensed eye will be included in the FAS for eye level analyses. The FAS will be used for all efficacy analyses in subject level and eye level data.

The Safety Analysis Set will consist of all dispensed subjects or eyes. If only one eye is dispensed, the subject will be included in the Safety Analysis Set for subject level summaries, but only the dispensed eye will be included in the Safety Analysis Set for eye level summaries. All safety analyses and summaries will be based on the Safety Analysis Set.

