6.5.10.2 Primary Efficacy

The primary effectiveness analysis will be performed based on the FAS. The primary endpoint is evaluated as the responder status based on subjects' responses to the statement "Clear vision: near, far, and in-between' in the online consumer survey, where a "responder" is defined as a participant agrees the statement. For the primary endpoint, the null hypothesis (H0) is that the proportion of subjects agreeing with the statement (π) is less than or equal to 0.5. The alternative hypothesis (H1) is that the proportion of subjects agreeing is greater than 0.5.

*H*₀:
$$\pi \le 0.5$$

*H*₁: $\pi > 0.5$

The responses to the primary endpoint statement will be summarized using categorical summary statistics (strongly agree, agree, slightly agree, neither agree nor disagree, slightly disagree, disagree, strongly disagree).

Responses of strongly agree, agree, and slightly agree will be coded to a category "Agree." Responses of strongly disagree, disagree, and slightly disagree will be coded to a category "Disagree." The trichotomized responses will be summarized categorically (agree, neither agree nor disagree, disagree).

Neutral responses (i.e., "neither agree nor disagree") will not be included in the primary statistical analysis. The non-neutral responses used for the analysis will be presented using categorical summary statistics (agree, disagree). An exact 95% confidence interval (Clopper-Pearson test) around the proportion of subjects agreeing with the statement will be presented along with the p-value from a one-sided exact binomial test of the alternative hypothesis is that the proportion of subjects agreeing is greater than 0.5.

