6.5.13 Determination of Sample Size

Approximately 300 subjects will be enrolled. Allowing for up to 10% losses, power calculations were completed for 270 completed subjects. An exact binomial test with a nominal 5% one-sided significance level will have 93% power to detect the difference between the Null hypothesis proportion, π_0 of 0.5 and the Alternative proportion, π_1 , of 0.6 when the sample size is 270.

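### The primary analysis drops dispensed subjects who stop for poor vision before the survey, which biases the agreement proportion upward for the dispensed population

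*SAP*

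**What the plan says.** - **Analysis set.** SAP 6.5.1: "The Full Analysis Set (FAS) will consist of all eligible, dispensed subjects or eyes".
- **Missing answers.** SAP 6.5.11.1: "The primary efficacy analysis will be conducted using the FAS and missing values will not be imputed". Protocol 7.1.7 and 7.8.3 agree. SAP 6.5.10.1 bases percentages on non-missing values unless otherwise specified, and SAP 6.5.10.2 also removes neutral answers from the primary test.
- **Timing.** Under SAP 6.4.1 the survey is completed at least 7 days after the 1-Week visit and before the 3-Week visit. Protocol 5.2.2 lets a late subject complete it at the 3-Week visit. It is not among the Exit Visit steps in Protocol 5.1.4, and SAP 6.5.2 summarizes survey data from scheduled visits only.
- **Stopping.** The reasons for discontinuation in Protocol 3.3.3 include "Unacceptable contact lens visual acuity (VA". The same list has persistent study-related symptoms or complaints, and unacceptable centration and movement. Discontinued subjects are not replaced. For those who stop, Protocol 5.1.4 tells the site to "indicate the PRIMARY exit reason for each eye on the Subject Exit Form".
- **Sensitivity.** SAP 6.5.11.1 plans a best case, a worst case (every missing answer set to Disagree) and, if the primary analysis is significant and the worst case is not, a tipping-point analysis.
- **Gate.** In SAP 6.5.11.4, testing of the Holm family depends only on rejecting the primary null hypothesis.

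**The concern.** The statement being rated is about clear vision at near, far and in between. A subject who gives up the lens in the first two weeks because vision is unacceptable is very likely to disagree with it, yet has no planned chance to say so. The missing answer is then caused by the outcome itself. What the primary analysis estimates is agreement among those who kept wearing the lens long enough to be asked, although the SAP names all dispensed subjects as the population.

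Two things depend on this: the reported agreement percentage, and the test that opens the supportive survey and investigator claims. The planned sensitivity analyses show how far the result could move, but they leave the primary estimate as it is, and the SAP does not say what follows if the worst case fails.

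**Working it through.** **Inputs from the documents.** Null: proportion agreeing "is less than or equal to 0.5" (SAP 6.5.10.2). Alternative: "of 0.6 when the sample size is 270" (SAP 6.5.13). Losses: "Allowing for up to 10% losses, power calculations were completed for 270 completed subjects" (SAP 6.5.13), from about 300 enrolled.

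**Assumptions, not in the documents.** 300 dispensed; no neutral answers; *m* subjects stop over vision before answering; a share *d* of them would have disagreed.

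**1. The plan's own figure.** The SAP says: "An exact binomial test with a nominal 5% one-sided significance level will have 93% power". For n = 270 the smallest count *r* with P(X ≥ r | 270, 0.5) ≤ 0.05 is 150 (size 0.0387; 149 gives 0.0501). Power is P(X ≥ 150 | 270, 0.6) = 0.939. The stated 93% reproduces.

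**2. When the survey can be answered.** The 1-Week visit window is Day 6 to 10 (Protocol 3.6). Adding 7 days gives Day 13 to Day 17 as the earliest survey day. A stop before that leaves no answer.

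**3. Size of the bias.** If all *m* leavers would disagree, the complete-case proportion exceeds the all-dispensed proportion by (observed proportion) × m/300. At about 60% observed this is 0.6 points for m = 3, 1.2 for m = 6 and 3.0 for m = 15.

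**4. Effect on the test at the null.** Let exactly 150 of 300 dispensed subjects truly agree. Responders then agree with probability p = (150 − (1 − d)m)/(300 − m). The rejection probability is P(X ≥ r | 300 − m, p), with *r* the critical count for 300 − m.

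| m (of 300) | n | r | size at p = 0.5 | rejection, d = 1 | rejection, d = 0.75 |
|---|---|---|---|---|---|
| 3 (1%) | 297 | 164 | 4.1% | p = 0.5051: 5.8% | p = 0.5025: 4.9% |
| 6 (2%) | 294 | 162 | 4.5% | p = 0.5102: 9.0% | p = 0.5051: 6.5% |
| 15 (5%) | 285 | 157 | 4.9% | p = 0.5263: 22.0% | p = 0.5132: 11.2% |
| 30 (10%) | 270 | 150 | 3.9% | p = 0.5556: 52.5% | p = 0.5278: 19.7% |

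The last row is an extreme bound: it spends the plan's whole loss allowance on vision-related stops.

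**5. When the conclusion can change.** With 30 answers missing, the primary analysis needs 150/270 = 55.6%. The worst case needs 165/300 (p = 0.047), which is 165/270 = 61.1% of responders. The two disagree only for 150 to 164 agreeing, that is 55.6% to 60.7% observed.

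**6. An example at the design alternative.** 162/270 = 60% gives p = 0.0006. Worst case: 162/300 = 54%, p = 0.092. In the SAP's tipping-point procedure *k* missing answers become Disagree and the other 30 − k become Agree, so the count is (192 − k)/300. At k = 27 it is 165/300, p = 0.047; at k = 28 it is 164/300, p = 0.059. The result flips at 28 Disagree and 2 Agree.

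**The case against.** The strongest reply is that SAP 6.5.11.1 already deals with this. The worst case is harsher than any rule based on exit reason, so a result that survives it survives such a rule too. At 80% observed agreement with 30 missing, the worst case is 216/300 = 72% and p is below 10⁻¹³. This stands as far as the test is concerned: the bias is bounded, and it matters to the conclusion only in a narrow band. It does not correct the estimate: 80% would be reported where the all-dispensed figure could be as low as 72%.

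The plan also makes early vision-related stops less likely. Subjects are adapted multifocal wearers (Protocol 3.3.1.1), lenses are refined at dispensing and at Week 1 (5.1.1, 5.1.2), and a subject who answered before stopping may stay in the analysis. These points lower the likely *m*, but do not make it zero.

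Three stronger readings are tempting, and the documents do not support them:

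- *That the type I error is 53% at a planned 10% dropout.* The 10% is a ceiling for losses of any kind from enrolment. Protocol 3.1 and 3.3 give every consented subject an ID and treat that as enrolment, so the 30 can include people never dispensed and never in the FAS. If 30 are lost but only a quarter or a half for lens-related reasons, all of whom disagree, with the rest missing at random, rejection is 8.9% or 18.4%.
- *That any lens-related stop means Disagree.* Discomfort, poor centration, poor movement or a device-related adverse event does not imply disagreement about clear vision.
- *That 162/270 flips once 25 losses are counted.* 162/295 gives p = 0.051, but that leaves five subjects missing. It is not the SAP's procedure, which flips at 28.

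**Conclusion.** The concern holds for vision-related stops before the survey. The primary analysis is complete-case within the FAS, and leaving out subjects who stop over vision biases the agreement proportion upward for the dispensed population. Under the stated assumptions (300 dispensed, no neutral answers, true agreement exactly 50%), rejection is about 6%, 9% and 22% at 1%, 2% and 5% dropout if all such leavers disagree. It is about 5%, 6.5% and 11% if 75% do. The dropout rate is assumed throughout.

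This is a question of which analysis should be primary and should open the gate to the supportive tests. A reader might infer that the bias goes unexamined or that a positive result would be unsafe; neither follows, because the worst case is prespecified and high observed agreement would survive it. The change is worth making because the bias falls on the headline percentage whatever the p-value, and because nothing in the SAP makes the worst case count.

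**What to change.** In SAP 6.5.10.2 and 6.5.11.1:

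1. Count as Disagree in the primary FAS analysis any dispensed subject who discontinues before answering with a vision-related primary exit reason in either eye (unacceptable lens VA, or vision symptoms or complaints).
2. Add a sensitivity analysis that treats stops for comfort, centration, movement or a device-related adverse event the same way.
3. Keep the best-case, worst-case and tipping-point analyses for the remaining missing answers.
4. Report missing answers by exit reason.

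**Cost.** The primary exit reason is already recorded, so this should need SAP wording only; the form's categories are not in the documents, so check that they separate vision from other reasons. The agreement percentage becomes slightly less favourable. For example, 171/285 = 60.0% with 15 vision-related stops becomes 171/300 = 57.0%, p = 0.009. The rule brings an investigator-recorded reason into a subject-reported endpoint in an open-label study. Protocol 3.3.3 does not require subjects who withdraw voluntarily to give a reason, so those without one stay missing and remain covered only by the sensitivity analyses.

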6.5.11.2 Interim Analyses

No interim analyses are planned during the course of the study.

6.5.11.3 Multicenter Studies

The clinical study will be conducted under a common protocol at multiple investigational sites with the intention of pooling the data for analysis. Every effort will be made to promote consistency in study execution at each investigational site. The uniformity of the primary endpoint responses (agree, disagree) among the sites will be evaluated using a chi-square test.

Subjects' responder status to the statement "Clear vision: near, far, and in-between' in the online consumer survey will be summarized categorically at the subject level ('Agree' or 'Disagree') by site for the FAS. The denominator for percentages will be the number of non-missing values. Missing data will not be imputed.

Page 26 of 44 - CONFIDENTIAL

If any site has fewer than five subjects, that site will be pooled with the site with the fewest subjects, until a pooled site includes at least five subjects.

A chi-square test will be used to evaluate the consistency of the primary endpoint responses among the sites after pooling. If 25% or more of the cells have expected counts less than 5, then Fisher's exact test may be used instead. If the p-value from this test is less than 0.05 then the difference between sites will be considered statistically significant.

6.5.11.4 Control of Multiplicity

The primary endpoint is a single test, so multiplicity control is not necessary for this evaluation. The study will require the primary effectiveness endpoint to be statistically significant in order to test other endpoints. Specifically, failure of the primary effectiveness endpoint will invalidate the statistical significance of the supportive effectiveness endpoints.

For the online survey and investigator questionnaire inferential tests on the FAS including all subjects, the risk of type I errors will be controlled as follows:

- These supportive effectiveness outcomes will not be eligible for statistical hypothesis testing unless the null hypothesis is rejected for the primary endpoint.
- The Holm adjustment will be applied. The following tests will be included in the Holm procedure:

The proportion of subjects agreeing with the statement:

- o Provide effortless vision
- Provide clear vision from near to far seamlessly throughout the day
- Provide all-day comfort and continuously clear vision
- o Provide clear vision, even in low light
- Help reduce stress and tiredness in my eyes
- Allow me to effortlessly move from various tasks throughout the day
- \circ Help prevent my eyes from feeling tired and fatigued at the end of the day
- o Help protect against irritation and discomfort
- o Make my eyes feel relaxed Are so breathable, the lenses feel like air

Page 27 of 44 - CONFIDENTIAL

- Provide clear vision when driving at night
- Help my eyes feel healthy
- Feel continuously moist
- Help support changes in my eyes that occur with age
- Give me freedom from reading glasses
- Feel incredibly soft, smooth, and weightless
- Give me the freedom to do more in life
- Provide a new visual experience to see life full of color and vibrancy
- Help me live life to the fullest
- Are comfortable
- Help eyes stay moist
- o Provide clear vision
- o Prevent blurriness
- Prevent eyes from feeling dry
- Prevent eyes from feeling tired or fatigued

The proportion of subjects for whom the investigator

- was completely, very satisfied, or somewhat satisfied with the use of the contact lenses by the subject
- o agrees that the lens was easy to fit for the subject
- o agrees that the lenses deliver clear vision for the subject
- o agrees that the lens helps maintain a smooth, wettable surface for the subject
- reports that it was extremely simple, simple, or somewhat simple to successfully fit the contact lens for the subject

Page 28 of 44 - CONFIDENTIAL

- o agrees that the fitting process for the lens was straightforward for the subject
- reports that it was extremely easy, easy, or somewhat easy to successfully fit the lens during the first visit for the subject

